7.6. Study Commencement

Upon satisfactory receipt of all necessary paperwork, Keryx or its official designee will arrange for all study material to be delivered to the study center. Subjects must not undergo study procedures, that is, sign a consent form, until appropriate initiation activities have occurred. Initiation activities will include the training of personnel expected to be involved in the study conduct and will include review of the study protocol, instructions for electronic Case Report

Form (eCRF) completion and serious adverse event (SAE) reporting, and overall responsibilities, including those for drug accountability and Study Master File maintenance.

8. SELECTION AND WITHDRAWAL OF SUBJECTS

8.1. Subject Inclusion Criteria

Subject eligibility should be reviewed and documented by an appropriately qualified member of the Investigator's study team before subjects are included in the study.

Subjects must meet all of the following inclusion criteria to be eligible to participate in this study:

1. Age \geq 18 years
2. Men and women. Women of childbearing potential must have a negative serum pregnancy test at Screening
3. eGFR \geq 20 mL/min and $<$ 60 mL/min at Screening
4. Hgb \geq 8.5 g/dL and \leq 11.5 g/dL at Screening
5. Serum ferritin \leq 500 ng/mL and TSAT \leq 25% at Screening
6. Serum iPTH \leq 600 pg/mL at Screening
7. Must consume a minimum of 2 meals per day
8. Willing and able to give written informed consent
9. Female subjects who are not surgically sterile (by bilateral tubal ligation, bilateral oophorectomy, or hysterectomy) or postmenopausal (no menstrual period within 1 year of Screening) must agree to use adequate contraception throughout the study and for at least 4 weeks following their final study visit. Adequate contraception is defined as:
 - a. Total abstinence from sexual intercourse starting at least 1 complete menstrual cycle prior to Screening visit, or
 - b. Having a vasectomized partner, or
 - c. Use of hormonal contraceptives (oral, parenteral, or transdermal) for at least 3 months prior to study drug administration or intrauterine contraception/device, or
 - d. Use of a double-barrier method (such as male condom, female condom, diaphragm, sponge, or cervical cap *together with* spermicidal foam/gel/film/suppository) starting at Screening

There is no restriction for female partners of male subjects.

8.2. Subject Exclusion Criteria

Subjects will be excluded if they meet any of the following criteria:

1. Serum phosphate $<$ 3.0 mg/dL at Screening
2. Liver transaminases (ALT or AST) $>$ 3 \times upper limit of normal at Screening
3. IV iron administered within 4 weeks prior to Screening or during the Screening Period
4. ESA administered within 4 weeks prior to Screening or during the Screening Period
5. Blood transfusion within 4 weeks prior to Screening or during the Screening Period

6. Treatment with any investigational drug within 4 weeks prior to Screening or during the Screening Period
7. Cause of anemia other than iron deficiency anemia of CKD
8. Symptomatic gastrointestinal bleeding within 12 weeks prior to Screening or during the Screening Period
9. Symptomatic inflammatory bowel disease within 12 weeks prior to Screening or during the Screening Period
10. Dialysis within 12 weeks prior to Screening or during the Screening Period, or initiation of dialysis planned within 6 months following Screening
11. Kidney transplant recipient or kidney transplant scheduled within 6 months following Screening
12. Planned surgery or hospitalization (anticipated to last >72 hours) in the 6 months following Screening other than dialysis access-related surgery
13. Requires treatment with myelosuppressive therapy and/or immunosuppressive therapy at Screening or during the Screening Period
14. Requires treatment with oral corticosteroids at Screening or during the Screening Period (use of low-dose oral corticosteroids, eg, ≤ 5 mg/day prednisone or the relative equivalent dose of another corticosteroid, is not an exclusion); IV corticosteroids administered within 2 weeks prior to Screening or during the Screening Period.
15. Active infection requiring treatment with antibiotics at Screening or during the Screening Period
16. Malignancy except for subjects that have been disease-free for at least 2 years after curative therapy or non-melanoma skin cancer regardless of treatment
17. History of hemochromatosis
18. Subjects who are pregnant or breast feeding
19. Active drug or alcohol dependence or abuse (excluding tobacco use or medicinal or recreational marijuana use where legal unless there is evidence of abuse) within the 12 months prior to Screening or evidence of such abuse (in the opinion of the Investigator)
20. Subjects with known allergic reaction to previous oral iron therapy
21. Prior treatment with KRX-0502
22. Any other medical condition that, in the opinion of the Investigator, renders the subject unable or unlikely to complete the study or that would interfere with optimal participation in the study or produce significant risk to the subject

8.3. Subject Withdrawal Criteria

8.3.1. Discontinuation From Study Drug

Discontinuation from study drug is defined as a permanent termination of treatment with KRX-0502. Subjects may be discontinued from the study drug at any time for any of the following reasons:

- Adverse event
- Lack of efficacy (see [Section 9.2.2](#))
- Pregnancy
- Withdrawal by subject
- Other

If at any time during the course of the study, in the opinion of the Investigator, the subject may no longer safely participate due to a change in medical status (eg, experiences an AE, becomes pregnant), the subject must be discontinued from the study drug.

Whenever study drug is discontinued prematurely, Keryx and the Medical Monitor must be notified. The subject should return for the ET visit and exit the study.

8.3.2. Discontinuation From Study

Subjects may discontinue from the study for the following reasons:

- Discontinuation from study drug (see Section 8.3.1)
- Subject withdrawal of consent
- Lost to follow-up
- Study drug non-compliance
- Investigator judgment
- Use of certain prohibited therapies (see [Section 9.2.1](#) and [Section 9.2.2](#))
- Start of chronic dialysis or kidney transplantation
- Death
- Sponsor termination of study
- Other

The Investigator should inquire about the reason for withdrawal, request the subject to return all unused investigational product, request the subject to return for a final ET Visit as soon as possible to undergo the assessments specified for the visit, and follow-up with the subject regarding any unresolved AEs. For ETs that occur on or after the day of study drug initiation, every effort should be made to document the subject's outcome, regardless of cause. Whenever a subject is discontinued prematurely, Keryx and the Medical Monitor must be notified.

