15.2. Determination of Sample Size

Because this is an open-label Phase 4 study designed to estimate within-group changes from Baseline and describe time trends of iron parameters in sub-groups of subjects, it is appropriate to conduct a precision-based sample size estimation as opposed to a power-based calculation. The primary endpoint of interest is change in Hgb from Baseline at Week 24. The SD for that endpoint is estimated as 0.9 g/dL based on the Week 16 data in a prior Phase 3 study in a similar population (Study 306).

Assuming a population SD of 0.9 g/dL, with a sample size of 140 subjects, the 95% confidence intervals (CIs) for mean change in Hgb from Baseline to Week 24 can be estimated, allowing for a CI half-width of 0.149 g/dL.

It is assumed that 30% of the subjects in this study will drop out or be otherwise excluded from the PP population. Hence, 200 subjects will be randomized to ensure that there will be sufficient subjects at the end of the study for the longitudinal analyses (ie, 70 evaluable subjects in each randomized treatment group). Based on prior clinical trial experience, it is estimated that half of the subjects will stay on their starting dose, and the other half will increase their dose after 12 weeks of treatment. Hence, it is expected that the 4 dosing sequence groups that will arise will have approximately equal numbers of subjects (ie, 35 subjects are expected in each of the four dosing sequence groups (3-3, 3-6, 4-4, and 4-6 tablets/day).

The proposed sample size and the sizes of the sub-groups of interest are deemed sufficient for the analyses proposed below including the longitudinal analyses.

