15.10. Other Statistical Issues

15.10.1. Significance Levels

Unless otherwise specified, all tests will be 2 tailed using a 0.05 level of significance. All CIs will be 2-sided 95% CIs.

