- L, if Study Day is the subject's last study medication dose date and
- P, if Study Day is after the subject's last study medication dose date.

The derivation of study day is outlined in section 6.5.2.

11. In the listings, any subject who is a 'protocol permitted ESA rescue therapy user' will be identified with an asterisk.

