**Table 2: Visit Windows (Study Days)**

Visit Number: Visit Name	Analysis Visit Name	Relative Target Day (Study Day)	Visit Window (Study Day Interval)
Visit 1A: Screening a	Screening	-14	<1
Visit 1A: Retest a	Screening	-9 a	<1
Visit 1B: Rescreen b	Screening	-14 b	<1
Visit 1B: Retest b	Screening	-9 b	<1
Visit 2: Randomization	Baseline	1	1
Visit 3: Week 2	Week 2	15	[2, 22]
Visit 4: Week 4	Week 4	29	[23, 43]
Visit 5: Week 8	Week 8	57	[44, 71]
Visit 6: Week 12	Week 12	85	[72, 99]

Document: \\quintiles.net\enterprise\apps\sasdata\sasb\sas\Keryx\KRX-0502\Biostatistics\Documentation\SAP\

Visit Number: Visit Name	Analysis Visit Name	Relative Target Day (Study Day)	Visit Window (Study Day Interval)
Visit 7: Week 16	Week 16	113	[100, 127]
Visit 8: Week 20	Week 20	141	[128, 155]
Visit 9: Week 24	Week 24	169	[156, 197]
Visit 10: Week 32	Week 32	225	[198, 253]
Visit 11: Week 40	Week 40	281	[254, 309]
Visit 12: Week 48	Week 48	337	>309
Visit Early Termination: Early Termination (ET) c	Early Termination		

a Any retest for specific inclusion and exclusion criteria that were not met at the initial testing may occur within 10 days of the original screening date. Therefore, the visit window, including start and end dates, for the retest is the same visit window as that for the original screening visit. A subject can have only 1 retest based on the original screening results.

b Visit window for the rescreen visit has a study day interval relative to Day 1, equivalent to that for the original screening visit but because rescreening of a subject must be at least 14 days after the subject's original screen failure date the actual start and end dates on a subject's Screening Visit window and the Re-Screening Visit window differ. A subject can have only 1 retest based on the re-screening results. Any retest for specific inclusion and exclusion criteria that were not met at re-screening may occur within 10 days of the re-screening date.

c Early Termination visits may fall within a visit window corresponding to a planned study visit. If this is the case, the ET visit will be labeled and summarized with the analysis visit name corresponding to the visit window.

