Multiple assessments may occur within the same window for a variety of reasons, for example, assessments to determine if the study drug dose should be adjusted. While there is only one planned scheduled dose adjustment, unscheduled dose adjustments for a subject may be necessary at any time during the study.

The protocol includes guidance on making dosing adjustments which are dependent on specific central laboratory results. Laboratory values will be checked at each scheduled visit and the study drug dose may be adjusted in response to these results. When laboratory retesting is necessary, it will be done as an unscheduled visit, unless it coincides with a scheduled visit.

Given the time lag in obtaining lab results and communicating the desired dose adjustment to the subject via telephone the time that the new prescription is to start and the subsequent follow-up blood draws for testing may or may not be in a single window for an originally planned visit given in the protocol's schedule of assessments. There may be multiple assessments falling in the same window and multiple assessments related to a single event may be taken during the window for more than one scheduled visit.

Additionally, when a subject discontinues from the study, the assessments made at the Early Termination visit may fall within a window for one of the originally planned visits given in the protocol's schedule of assessments.

When multiple assessments occur within the same window, the one whose date of assessment is the largest study day in the window will be considered as the observed assessment value for that scheduled visit study day.

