## 9.6. Summary of Changes from Protocol-Specified Analyses

- The protocol states that “All subjects who are randomized and take at least 1 dose of study medication will be included in the Safety Analysis Set.” However, the Safety Analysis Set is being defined as the set of all subjects who receive at least one dose of study medication, to allow for the highly unlikely possibility that some subject (s) may receive a dose of medication prior to being randomized.
- The protocol did not discuss the potential for an ad hoc analysis. The analysis is acknowledged in this SAP and more details will be added to an amended SAP if an analysis is performed.
- The protocol did not discuss the modified Per Protocol Analysis Set. This analysis set is described in section 6.3.6 and is used for the 24-Week analysis snapshot only.
- The SAP describes analyses for the following secondary efficacy endpoints which were not included in the protocol:
  - Time from randomization to first hemoglobin increase of  $\geq$  0.5 g/dL from Baseline.
  - Change from the baseline value for each of the following:
    - eGFR
    - serum bicarbonate
    - intact parathyroid hormone
    - C-terminal fibroblast growth factor 23
    - intact fibroblast growth factor
  - Inclusion of box and scatter plots over time of the observed value and the change from Baseline for each of the iron parameter efficacy variables, TSAT and ferritin to explore the question of their stability over time on treatment.
- The protocol specified analyses of vital signs is not included in the SAP, since no related safety concerns are anticipated.

- The protocol states that all efficacy analyses will be performed based on both the FAS and the PP/mPP analysis sets, however only the PP/mPP analyses sets will be considered. Subjects are excluded from the PP/mPP analysis sets due to confounders of efficacy and thus the FAS is not appropriate for efficacy analyses. The FAS will be used for the efficacy analysis for the 'Permitted' ESA Rescue Therapy subgroup.
- The protocol did not include the baseline by visit interaction term in the efficacy model. This interaction term is included in the SAP and will be included in the model.
- Missing endpoint observations will not be imputed using a multiple imputation (MI) linear regression approach for use in an additional sensitivity analysis as specified in the protocol sections 15.7.2 and 15.10.3.

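### SAP 6.5.4 lets Early Termination labs drawn after permanent drug stop, dialysis or transplantation stand as planned-visit values, even in place of an on-drug value, in the laboratory MMRMs

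*Protocol*

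**What the plan says.** **Recall.** Protocol 8.3.1 sends a subject who stops drug prematurely to the ET visit and then out of the study. Protocol 8.3.2 lists "Start of chronic dialysis or kidney transplantation" among the reasons for leaving, and for all such exits asks the site to "request the subject to return for a final ET Visit as soon as possible to undergo the assessments specified for the visit". No maximum interval in days is set. Protocol 10.6.2 gives the ET labs: CBC, chemistry, iron studies, iPTH and FGF23.

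**Mapping.** Under SAP Table 2, footnote c, if an ET draw falls in a planned window, "the ET visit will be labeled and summarized with the analysis visit name corresponding to the visit window". SAP 6.5.4 adds that when a window holds several assessments, "the one whose date of assessment is the largest study day in the window will be considered as the observed assessment value". SAP 6.5.2 counts study day from randomization up to the end of treatment, but from the treatment end date after that.

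**Analysis.** SAP 8.2 and 8.3 fit MMRMs to Hgb, TSAT, ferritin, phosphate, eGFR and bicarbonate by visit in the PP set (mPP for the 24-week snapshot). SAP 9.6 explains the choice of sets: "Subjects are excluded from the PP/mPP analysis sets due to confounders of efficacy". The exclusion lists in SAP 6.3.5 and 6.3.6 name transfusion, ESA, IV iron, pregnancy and major eligibility violations, plus compliance below 50% for PP only. Neither list names dialysis, transplantation or time off drug. Post-dose draws do carry a marker ("P, if Study Day is after the subject's last study medication dose date"), but SAP 6.2 defines it for listings only.

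**The concern.** The per-protocol analyses are meant to describe the response on KRX-0502 without outside influences. A single ESA dose removes a subject entirely, yet a phosphate drawn after dialysis has started, or an eGFR drawn after a transplant, may enter the model as an ordinary visit value. An ET draw some time after the last tablet may also overwrite the scheduled on-drug value for the same visit, including Week 24, the visit of the primary endpoint.

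No other planned analysis would reveal this. SAP 9.6 drops both the general FAS efficacy analyses and the multiple-imputation sensitivity analysis. If the SAP stays silent, the handling of these values will be settled during programming or data review, when the values can be seen.

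**Working it through.** **1. The plan's own precision figure.** Inputs: SD and n from Protocol 15.2 ("Assuming a population SD of 0.9 g/dL, with a sample size of 140 subjects") and Protocol 15.10.1 ("All CIs will be 2-sided 95% CIs"). Half-width = 1.96 × 0.9 / √140 = 0.149 g/dL, as stated. 140 / (1 − 0.30) = 200, also as stated.

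**2. Where an ET draw lands, counting from randomization.** The Table 2 windows are [2, 22], [23, 43], [44, 71], [72, 99], [100, 127], [128, 155], [156, 197], [198, 253], [254, 309] and >309. Each starts the day after the previous one ends and the last is open, so every ET draw from day 2 onward falls in an analysed visit.
- Drug stopped day 150, ET on day 164: this is the subject's Week 24 value.
- Scheduled Week 24 visit on day 169, drug stopped day 175, ET on day 189: both draws lie in [156, 197], and since 189 > 169 the off-drug value replaces the on-drug one.

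**3. Where it lands under SAP 6.5.2 read literally.** In the two examples the study day is 164 − 150 + 1 = 15 and 189 − 175 + 1 = 15, so both draws go to Week 2. In general an ET draw 1 to 21 days after treatment end becomes day 2 to 22, exactly the Week 2 window. There it replaces a true Week 2 value drawn on any smaller study day. The same reading would send a completer's Week 48 draw on day 337, the morning after a last dose on day 336, to 337 − 336 + 1 = day 2. That cannot be intended.

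**4. Size for Hgb at Week 24 (illustrative).** Assumptions: T early terminations among 200 subjects, spread evenly over 336 days; every ET draw in the 42-day Week 24 window is off drug; each is lower than the on-drug value by 0.25 to 0.84 g/dL. The upper figure is the Study 306 difference from placebo at Week 16 (Protocol 5.2), used as a ceiling. Values in window = T × 42/336; subjects remaining = 200 − T × 155/336; shift in mean = share × loss.

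| T | ET values in window | Remaining | Share | Shift at 0.25 | Shift at 0.84 |
|---|---|---|---|---|---|
| 20 | 2.5 | 190.8 | 1.3% | 0.003 | 0.011 |
| 40 | 5.0 | 181.5 | 2.8% | 0.007 | 0.023 |
| 60 | 7.5 | 172.3 | 4.4% | 0.011 | 0.037 |

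The largest shift is 0.037 / 0.149 = 25% of the half-width. This is the direct effect only. An off-drug value at an earlier visit also acts through the model's prediction for that dropout. A TSAT simulation with assumed inputs (10 to 25% of subjects ending on an off-drug value that has lost 25 to 75% of an 18.4-point effect) gave a bias of 0.24 to 1.4 points toward no effect. Scaled by 0.84/18.4, that is about 0.01 to 0.06 g/dL.

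**5. Size for eGFR (illustrative).** Shift in an arm of 70 = k × Δ / 70, with k post-transplant values at the visit and Δ the assumed rise. For k = 1: Δ = 10 gives 0.14, Δ = 20 gives 0.29, Δ = 30 gives 0.43 mL/min/1.73 m². Three values at Δ = 30 give 1.29. The documents supply neither Δ nor k.

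**6. Precision lost by setting values aside.** 0.149 / √(1 − f): f = 2%, 5%, 10% gives 0.151, 0.153, 0.157 g/dL.

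**7. The ANCOVAs.** SAP 8.3 limits the Hgb, iPTH and FGF23 ANCOVAs to subjects who complete the visit concerned (Table 3 marks completers for Hgb only). What mainly remains is a Week 24 completer whose ET draw falls by day 197.

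**The case against.** **Using ET values is a legitimate choice.** A treatment-policy analysis would keep values after drug stop, and Protocol 8.3.2 wants outcomes documented whatever the cause of exit. Subjects may stop for an adverse event or lack of efficacy. Deleting their last values leaves the missing-at-random model to predict them as if they had stayed on drug, which may flatter the result. This stands against any blanket deletion. A fixed cut-off such as 7 days after last dose also has no basis in the documents. It does not excuse silence, nor replacing an on-drug value in the same window.

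**The PP definition may already cover dialysis and transplantation.** SAP 6.3.5 has a general clause about added treatment that undermines the efficacy measurements. SAP 6.3.6 omits it, yet says compliance is the sole difference between PP and mPP. A reader might infer that mPP has no such protection; the text is ambiguous rather than clear either way. If applied, the clause removes the whole subject with all valid earlier data, and it does not address an off-drug draw.

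**Two stronger readings do not hold.** A reader might infer that iPTH and FGF23 results are broadly contaminated; the completer restriction leaves only a narrow route. A reader might also infer a sizeable TSAT bias. The 18.4-point effect comes from Study 306, where dosing could reach 12 g/day, against at most 6 here. The simulation's SD (12), correlation (0.6) and loss of effect have no source in the documents. Having 25% of subjects end on off-drug values would use most of the 30% allowance, which also covers PP exclusions. Even the largest simulated bias, 1.4 points, lies inside the simulated half-width of 1.99.

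**Events may be few.** Entry requires eGFR of at least 20 and excludes dialysis planned, or a transplant scheduled, within 6 months of screening. Some early exits will yield no ET draw, and some ET draws will still be on drug.

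**Conclusion.** The gap is real and lies in SAP 6.5.4; the recall instruction in Protocol 8.3.2 is ordinary data collection. Two things are wrong as written: an off-drug ET value displaces an on-drug value in the same window, and SAP 6.5.2 restarts study day at treatment end, which defeats the visit windows. Stating how post-dialysis, post-transplant and lone off-drug values are handled is a cheap improvement.

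The documents do not support a claim that the primary result is materially distorted. The direct effect on the Week 24 Hgb mean is illustratively 0.003 to 0.037 g/dL, at most about a quarter of the 0.149 half-width. This rests on an assumed number, timing and depth of off-drug values. The indirect route through the model cannot be sized from the documents; the scaled simulation stays below half the half-width. For eGFR, phosphate and bicarbonate one dialysis or transplant value may weigh more, but the 0.43 figure is an assumption about a single value and no event rate is given.

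**What to change.** In SAP 6.5.4 and 6.6.1, for all laboratory efficacy models:

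1. Do not use values dated on or after the start of chronic dialysis or transplantation; use the last earlier value in the window, if there is one. State in 6.3.5 and 6.3.6 that these subjects stay in PP and mPP with their pre-event data. Show their number by group beside the eGFR table, so that loss of kidney function is not hidden.
2. Where a window holds both an on-drug value and an ET value drawn after permanent discontinuation, let the on-drug value represent the visit. Define on-drug so that a trough draw on the morning after the last dose qualifies, as scheduled samples do under Protocol 7.1.
3. Where the only value in a window is an off-drug ET value, report the MMRM with and without such values rather than deleting by a fixed number of days.
4. Amend 6.5.2 so that study day for windowing is counted from randomization after treatment end as well. A separate count from last dose can serve the listings.

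Cost: SAP wording, one derivation and one added sensitivity run. Dose dates and exit reasons are already recorded; the start date of dialysis or the transplant date must be available to the programmers. A few values leave the main model. Even if 10% of Week 24 Hgb values were set aside, the half-width would rise only from 0.149 to 0.157 g/dL. Visits, safety tables and planned enrolment do not change.
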